7.5. Criteria for Study Termination

Sage Therapeutics may terminate this study or any portion of the study at any time for safety reasons including the occurrence of AEs or other findings suggesting unacceptable risk to participants, or for administrative reasons. In the event of study termination, Sage Therapeutics will provide written notification to the investigator. Investigational sites must promptly notify their IRB, where required, and initiate withdrawal procedures for participating participants.

8. SELECTION AND WITHDRAWAL OF PARTICIPANTS

8.1. Participant Inclusion Criteria

Participants must meet all of the following criteria to qualify for participation in this study:

1. Participant has signed an ICF before any study-specific procedures or washout of drugs is performed.
2. Participant is ambulatory and is 18 to 80 years of age, inclusive, at the time informed consent is obtained.
3. Participant has a diagnosis of ET, as defined by all of the following criteria:
 - a. Isolated tremor syndrome consisting of bilateral upper limb action tremor
 - b. At least 3 years duration
 - c. With or without tremor in other locations (eg, head, voice, or lower limbs)
 - d. Absence of other neurological signs, such as dystonia, ataxia, or parkinsonism, isolated focal tremors (eg, voice, head), task- and position-specific tremors, sudden tremor onset or evidence of stepwise deterioration of tremor
4. Participant scores at least 1.5 for each of the six items that comprise the combined total upper limb TETRAS (total performance subscale part 4) with the total score for the dominant upper limb (the sum of the three items for either the right or left upper limb, whichever is dominant) being at least 5.5, at both Screening and predose on Day 1.
5. Participant is willing to completely downtitrate and discontinue from medications taken for the treatment of ET at least 14 days or 5 half-lives (whichever is longer) prior to receiving IP. Medications taken for the treatment of ET that were discontinued prior to receiving IP may be resumed following Day 29.
6. Participant is willing to discontinue the use of alcohol and products that contain nicotine within at least 1 week prior to Day 1 and through Day 29 of the study.
7. Female participant agrees to use at least one method of highly effective contraception as listed in Section [9.2.4](#) during participation in the study and for 30 days following the last dose of study drug, unless she is postmenopausal (at least 12 months of spontaneous amenorrhea without an alternative medical cause, with confirmatory follicle stimulating hormone >40 mIU/mL), and/or surgically sterile (bilateral oophorectomy, hysterectomy, and/or bilateral salpingectomy), or does not engage in sexual relations which carry a risk of pregnancy (does include abstinence).
8. Male participant agrees to use an acceptable method of effective contraception for the duration of the study and for 13 weeks after receiving study drug, unless the participant does not engage in sexual relation(s) which carry a risk of pregnancy. Acceptable methods of effective contraception are listed in Section [9.2.4](#).
9. Male participant is willing to abstain from sperm donation for the duration of the study and for 13 weeks after receiving study drug.
10. Participant has no clinically significant findings, as determined by the investigator, on Screening and predose Day 1 physical examination including mental state examination (MSE) and neurologic examination, 12-lead ECG, or screening clinical laboratory tests.

8.2. Participant Exclusion Criteria

Participants who meet any of the following criteria are disqualified from participation in this study:

1. Participant has presence of known causes of enhanced physiological tremor.
2. Participant has had recent exposure (14 days prior to Day 1) to tremorgenic drugs or presence of alcohol withdrawal state.
3. Participant has had direct or indirect injury or trauma to the nervous system within 3 months before the onset of tremor.
4. Participant has had a previous procedure for the treatment of ET, deep brain stimulation, brain lesioning, or magnetic resonance (MR) guided procedure, eg, MR-guided focused ultrasound.
5. Participant has historical or clinical evidence of tremor with psychogenic origin (including but not limited to eating disorders, major depression, etc.)
6. Participant has currently active, medically significant hepatic, renal, cardiovascular, pulmonary, gastrointestinal, hematological, immunologic, ophthalmologic, metabolic (hypothyroidism with stable thyroid replacement is acceptable), or oncological disease.
7. Participant has history of substance abuse prior to Screening or has a positive screen for drugs of abuse at Screening or predose on Day 1 or has a positive screen for alcohol or cotinine predose on Day 1.
8. Participant has a known allergy to SAGE-324 or any excipient.
9. Participant has had exposure to another investigational drug or device within 30 days or 5 half-lives (if known) of the investigational drug, whichever is longer, prior to the Day 1 visit.
10. Participant has history or suicidal behavior within 2 years or answers “YES” to questions 3, 4, or 5 on the C-SSRS at Screening or at Day 1 or is currently at risk of suicide in the opinion of the investigator.
11. Participant has donated one or more units (1 unit = 450 mL) of blood or experienced acute loss of an equivalent amount of blood within 60 days prior to Day 1.
12. Participant has any condition or comorbidity that in the opinion of the investigator would limit or interfere with the participant’s ability to complete or partake in the study.
13. Participant is unwilling or unable to comply with study procedures and required training.
14. Participant has used any known moderate or strong cytochrome P450 3A4 inhibitors and/or inducers within 14 days or 5 half-lives (whichever is longer) prior to Day 1 or consumed grapefruit juice, grapefruit, Seville oranges, pomegranates, tangelos, or St. John’s Wort or products containing these within 30 days prior to Day 1. Use of mild cytochrome inhibitors and/or inducers may be permitted.
15. Participant has concurrent or recent exposure (14 days or 5 half-lives, whichever is longer, prior to the Day 1 visit) to sedative/hypnotic drugs, stimulants, highly caffeinated

beverages or dietary supplements containing high doses of caffeine, or recent increase above regular daily consumption of caffeine.

16. Participant plans to undergo elective surgery or relocate during participation in the study.
17. Participant is investigative site personnel or a member of their immediate families (spouse, parent, child or sibling whether biological or legally adopted).
18. [Removed]
19. Female participant has a positive pregnancy test or confirmed pregnancy.

8.3. Screen Failures

Screen failures are defined as participants who consent to participate in the clinical study but are not subsequently assigned IP or entered in the study, ie, a participant who does not meet 1 or more of the eligibility criteria after providing consent and prior to randomization (Day 1). A minimal set of screen failure information will be collected, including demography, screen failure details, eligibility criteria, and any SAE.

Individuals who do not meet the criteria for participation in this study (screen failure) may be rescreened.

8.4. Investigational Product Discontinuation and Early Termination from the Study

8.4.1. Investigational Product Discontinuation

A participant may discontinue IP at any time at his/her own request for any reason. The investigator may discontinue a participant from IP for safety, behavioral, compliance, or administrative reasons. Participants who discontinue IP will be encouraged by the investigator to remain on study and complete the EOT visit, the safety phone call 7 days later, and then, after a further 7 days, the End of Study/Early Termination visit (EOS/ETV), as specified in the Schedule of Assessments ([Table 2](#)). If the participant withdraws consent to collect protected health information, the EOS/ETV will be conducted.

The reason for IP discontinuation must be documented in the participant's study record and recorded in the participant's electronic case report form (eCRF).

The investigator must notify the sponsor and/or the medical monitor when a participant stops IP for any reason.

Participants who discontinue IP due to an AE, regardless of investigator-determined causality, should be followed until the event is resolved, considered stable, or the investigator determines the event is no longer clinically significant.

8.4.2. Early Termination from the Study

A participant may withdraw from the study at any time at his/her own request for any reason. The investigator may discontinue a participant from the study for safety, behavioral, compliance, or administrative reasons.

The reason for early termination from the study must be documented in the participant's study record and recorded in the participant's electronic case report form (eCRF).

The investigator must notify the sponsor and/or the medical monitor when a participant stops participation in the study for any reason.

If a participant is persistently noncompliant, the investigator should discuss with the sponsor the potential discontinuation of the participant. Any reasons for unwillingness or inability to adhere to the protocol must be recorded in the participant's eCRF, including:

- missed visits;
- interruptions in the schedule of study drug administration;
- non-permitted medications

If the participant withdraws from the study after completing 28 days of dosing with IP, they will be encouraged to attend follow-up visits for safety assessments at Day 35 and Day 42, as specified in the Schedule of Assessments ([Table 2](#)). If the participant withdraws their consent to collect protected health information, the EOS/ETV visit will be conducted and the participant will be permanently discontinued from the study at that time.

If the participant withdraws consent for disclosure of future information, the sponsor will retain and continue to use any data collected before such a withdrawal of consent.

If a participant withdraws from the study, he/she may request destruction of any samples taken and not tested, and the investigator must document this in the site study records.

8.4.3. Loss to Follow-up

A participant will be deemed lost to follow-up after 3 attempts at contacting the participant have been unsuccessful.

8.4.4. Replacement of Participants

Participants will not be replaced. However, additional participants may be enrolled if the drop-out rate is higher than 15%.

9. TREATMENT OF PARTICIPANTS

9.1. Description of Investigational Product

SAGE-324 is an orally administered tablet provided in 15 mg dose strengths. Participants will receive IP (60 mg total dose of SAGE-324 tablets, or appearance-matched placebo tablets) according to the randomization schedule. Additional details regarding IP preparation, formulation, and storage are included in Section 10.

9.2. Prior Medications, Concomitant Medications, Restrictions, and Contraception Requirements

9.2.1. Prior and Concomitant Medications and/or Supplements

The start and end dates, route, dose/units, frequency, and indication for all medications and/or supplements taken within 30 days prior to signing the informed consent through the first dose of IP will be recorded.

All medications and/or supplements taken from the first dose of IP through the Day 42 (± 1 days) visit (including start and end dates route, dose/units, frequency, and indication) will be recorded on the eCRF. Any concomitant medication determined necessary for the welfare of the participant may be given at the discretion of the investigator at any time during the study.

9.2.2. Prohibited Medications

Use or consumption of the following is prohibited for the timeframes specified:

- Treatment with an investigational drug or device during the 30 days or 5 half-lives (if known) of the investigational drug, whichever is longer, prior to Day 1 or during the study.
- Use of tremorgenic drugs within the 14 days or 5 half-lives (whichever is longer) of Day 1 or during the study.
- Use of agents known to affect SAGE-324 drug metabolism (any known cytochrome P450 3A4 inhibitors and/or inducers) within the 14 days or 5 half-lives (whichever is longer) of Day 1 and through Day 29 of the study period. Use of mild cytochrome P inhibitors and/or inducers may be permitted.
- Concomitant use of sedative/hypnotic drugs for 14 days or 5 half-lives prior to Day 1 and during the 28-day dosing period.
- Any prior ET medications must be discontinued prior to the Screening TETRAS:
 - There must be 14 days or 5 half-lives (whichever is longer) washout period prior to the Day 1 (baseline) visit.
 - For drugs requiring downtitration, there must be the required number of days for downtitration plus 14 days or 5 half-lives (whichever is longer) prior to the Day 1 (baseline) visit.

9.2.3. Other Restrictions

- Use of any drugs of abuse during the study period is prohibited. Note: participants with a history of drug abuse prior to screening should not be enrolled in the study.
- Use of alcohol within 1 week prior to Day 1 and through Day 29 of the study period is prohibited. If the alcohol test is positive on Days 1, 8, 15, 22, or 29, the participant will not be administered further IP and will be withdrawn from the study; no further efficacy assessments such as TETRAS will be undertaken.
- Use of products that contain nicotine within 1 week prior to Day 1 and through Day 29 of the study period is prohibited. Positive cotinine testing on Days 8, 15, 22, or 29 would be considered a major protocol deviation and the participant will be excluded from the Per Protocol Analysis Set. Positive cotinine testing on Day 1 is exclusionary.
- Consumption of grapefruit juice, grapefruit, Seville oranges, pomegranates, tangelos, or St. John's Wort or products containing these within 30 days prior to Day 1 and through Day 29 of the study period is prohibited.
- Use of stimulants, highly caffeinated beverages or dietary supplements containing high doses of caffeine within 14 days prior to the Day 1 visit and through Day 29 of the study period is prohibited. Note: participants should not increase their regular daily consumption of caffeine during the study period.

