7. INVESTIGATIONAL PLAN

7.1. Overall Study Design

This is a randomized, double-blind, placebo-controlled, parallel group study to evaluate the efficacy, safety, and tolerability of SAGE-324 in individuals with ET. Participants, site staff, and sponsor personnel will be masked to treatment allocation (see Section 9.5).

This study includes a Screening Period of up to 28 days, a 29-day treatment period consisting of 28 days of dosing with the end of treatment visit intended to be on Day 29 at trough, and a 14-day follow-up period relative to final dose (Figure 1). After providing informed consent, participants will undergo screening assessments as outlined in Table 2 to determine eligibility.

[figure not shown]
The Screening Period begins with the signing of the informed consent form (ICF). Eligible participants will visit the study center on Day 1 and complete additional eligibility assessments of safety and efficacy, as specified in the Schedule of Assessments (Table 2). Following completion of screening and Day 1 eligibility checks, participants will be randomized to 1 of 2 treatment groups (SAGE-324 60 mg daily, or placebo) in a 1:1 ratio.

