8.3.3.1.5. Subgroup Analyses of Primary and Key Secondary Endpoints

[figure not shown]
The TETRAS performance subscale part 4 upper limb tremor change from baseline total score (by side and combined), TETRAS performance total score, TETRAS performance subscale Part 4/6/7/8 score, and TETRAS ADL score will also be presented by the following subgroups:

- Age group: <65, 65-80 years
- Sex: Male, Female
- Race: White, Black or African American, Other
- BMI: <18.5, 18.5 - <25, 25-< 30, ≥ 30 kg/m²
- Age at essential tremor diagnoses: <40 years, 40-60 years, >60 years

- Age participant thinks essential tremor started: <40 years, 40-60 years, >60 years
- Years with essential tremor diagnosis: 3-<6 years, 6-10 years, and >10 years
- Years since participant thinks essential tremor started: 3-<6 years, 6-10 years, and >10 years
- Alcohol helps tremor: Yes (Intermediate, Worked Well), No (No, a little), NA
- Baseline TETRAS performance subscale part 4 upper limb tremor score: <12, >=12

If any of the subcategories has <5 patients fall into that category, that category should be combined with the next adjacent category with smaller counts. For example, if the number of patients fall into BMI category <18.5 is <5, this category should be combined with the 18.5 - <25 group.

Forest plots for subgroup analysis for change from baseline in TETRAS performance subscale part 4 upper limb tremor total score (by side and combined), TETRAS performance total score, TETRAS performance subscale Part 4/6/7/8 score, and TETRAS ADL total score at Day 29 – LS means, confidence interval – will be provided.

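### A positive alcohol test ends TETRAS collection, so a positive on Day 8, 15 or 22 removes the Day 29 primary score, and a positive on Day 29 can remove it

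*Protocol*

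**What the plan says.** All references are to Protocol Amendment 4, on which the SAP is based.

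- **Alcohol, Protocol 9.2.3.** A positive test at the Day 1, 8, 15, 22 or 29 visit has this consequence: "the participant will not be administered further IP and will be withdrawn from the study; no further efficacy assessments such as TETRAS will be undertaken".
- **Day 1, Protocol 8.2, exclusion 7.** A person who "has a positive screen for alcohol or cotinine predose on Day 1" is not eligible, so among randomised participants the rule should act only on Days 8, 15, 22 and 29.
- **Dosing and the primary visit, Protocol 7.1.** The treatment period has "28 days of dosing with the end of treatment visit intended to be on Day 29 at trough". The primary endpoint (Section 6) is the change in TETRAS part 4 on Day 29.
- **Nicotine, Protocol 9.2.3, next bullet.** A positive cotinine test after Day 1 costs membership of the Per Protocol set, and withdrawal is not mentioned. The text reads: "Positive cotinine testing on Days 8, 15, 22, or 29 would be considered a major protocol deviation and the participant will be excluded from the" (the sentence goes on to name that set).
- **Stopping IP, Protocol 8.4.1.** "Participants who discontinue IP will be encouraged by the investigator to remain on study and complete the EOT visit, the safety phone call 7 days" after that visit. The end-of-study visit comes 7 days after the call.
- **Leaving the study, Protocol 8.4.2.** The investigator may discontinue a participant for safety, behavioural, compliance or administrative reasons. Those who withdraw after 28 days of dosing are encouraged to attend safety follow-up on Days 35 and 42.
- **Alcohol as a tremor characteristic.** Protocol 12.1.1 records responsiveness to alcohol. SAP 8.3.3.1.5 uses it as a subgroup: "Alcohol helps tremor: Yes (Intermediate, Worked Well), No (No, a little), NA".
- **Missing data.** Protocol 13.2 allows no imputation. SAP 8.3.3.1.3 has one imputation sensitivity analysis: worst post-baseline value for listed reasons for ending treatment, including noncompliance with study procedures and physician decision, and LOCF otherwise. Alcohol-related withdrawal is not named.

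**The concern.** The rule ties together stopping IP, leaving the study and ending efficacy assessment. Only the first concerns exposure. The other two make the primary outcome missing, after randomisation, for a reason written into the protocol.

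That matters more if the loss is related to outcome. Participants whose tremor responds to alcohol, and whose tremor is not controlled, may be the ones who drink. If so, the missing Day 29 scores would tend to be poor ones, and could be more frequent in the arm that does less well. This is inference: the documents say nothing about how often tests will be positive, or in whom.

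The SAP leaves the analysis open as well. The estimand in SAP 4.1.1 and 8.3.3.1.1 gives no strategy for these withdrawals. In the imputation analysis the same event could receive the worst value or the last value, depending on how the reason is coded.

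**Working it through.** **1. What is lost, by day of the positive test**

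| Positive on | Effect of the assessment ban |
|---|---|
| Day 8 | Day 29 score lost. If the screen is read before that visit's TETRAS and Kinesia ONE, there may be no postbaseline efficacy assessment, and the participant leaves the Full Analysis Set (SAP 7.3). |
| Day 15 or 22 | Day 29 score lost; scores from earlier visits stay in the MMRM. |
| Day 29 | The last dose was on Day 28, so stopping IP has nothing to act on. The score is lost only if the screen is read before TETRAS. |

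The suggested order in the notes to the Schedule of Assessments (Table 2) is vital signs, TETRAS, Kinesia ONE, ECG, blood samples, questionnaires. The alcohol screen is not in the list.

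**2. Would the ordinary discontinuation path give a Day 29 score?** Under 8.4.1 the end-of-study visit falls 7 + 7 = 14 days after the EOT visit. If EOT is held on the day of the positive test, end of study falls on Day 22, 29 or 36 for a positive on Day 8, 15 or 22. SAP 8.3.2 maps Days 26 to 30 to Day 29, so only the Day 15 case would land in the window. That path does give TETRAS at EOT, but it does not promise a Day 29 score.

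**3. The plan's own power.** Inputs from Protocol 13.8 and SAP 5.2: difference 3, SD 3.5, 25 evaluable per arm, two-sided 0.05.

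- Normal approximation: 3 / (3.5 × √(2/25)) = 3.03; 3.03 − 1.96 = 1.07; power 85.8%.
- Two-sample t, 48 degrees of freedom: 84.4%.
- Stated: 85%. It reproduces.
- 60 × (1 − 0.15) = 51 evaluable, one more than the 50 required.

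**4. Power cost under assumed rates.** Each alcohol withdrawal is added to the 15% and counted as wholly non-evaluable, which is the worst case because the MMRM keeps earlier visits.

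| Assumed extra loss | Evaluable, of 60 | Power (t) | Randomised to keep 50 |
|---|---|---|---|
| 0% | 51 | 85.1% | 59 |
| 2% | 49.8 | 84.2% | 61 |
| 5% | 48 | 82.8% | 63 |
| 10% | 45 | 80.2% | 67 |

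If these losses fall inside the allowance, the planned power is unchanged: at 10%, 3 of 30 per arm are lost against an allowance of 0.15 × 30 = 4.5.

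**5. Bias under assumed rates.** Take the change from baseline as N(0, 3.5) on placebo and N(−3, 3.5) on SAGE-324 (mean, SD). Let the chance of losing Day 29 be h if the participant has not improved and 5% if improved. The proportion improved is 50% on placebo and Φ(3/3.5) = 80.4% on SAGE-324.

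- h = 20%. Loss on placebo: 0.5 × 0.20 + 0.5 × 0.05 = 12.5%. Loss on SAGE-324: 0.196 × 0.20 + 0.804 × 0.05 = 7.9%. Observed means −0.24 and −3.16; difference −2.92; bias 0.08 toward zero.
- h = 30%. Loss 17.5% and 9.9%. Observed means −0.42 and −3.27; difference −2.85; bias about 0.15 toward zero.

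These are observed-case figures at Day 29, not MMRM estimates, which also use the earlier visits.

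**The case against.** **Not scoring tremor under alcohol is a reasonable aim.** The plan treats alcohol as tremor-modifying and names somnolence as an adverse drug reaction, so handling it more strictly than nicotine is not in itself inconsistent. This stands. It does not explain why later visits without alcohol are also given up, and flagging a score deals with confounding without discarding it.

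**A reader might infer that every positive on Day 29 costs the primary score.** The documents do not support that. The rule bars only further assessments and TETRAS comes second in the suggested order, so the loss is possible, not certain.

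**A reader might infer a flat contradiction with 8.4.1.** That section only encourages participants to stay, and it schedules EOT, a call and end of study, not the remaining weekly visits. Section 8.4.2 allows the investigator to discontinue a participant from the study, and 9.2.3 can be read as a case of that. What remains is that no passage says which applies when IP is stopped for alcohol.

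**A reader might infer that safety follow-up is always lost.** Section 8.4.2 encourages Day 35 and Day 42 follow-up after 28 days of dosing, which covers the Day 29 case if a participant who is withdrawn by rule counts as one who withdraws. For earlier positives the text is unclear.

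**The size rests on assumed rates.** This stands. The protocol also allows extra enrolment if dropout exceeds 15%, which limits the power cost but does not restore the lost scores.

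**Conclusion.** The point holds. Under the current text a positive test on Day 8, 15 or 22 removes the primary Day 29 score by rule. A positive on Day 29 may remove it, depending on a sequence that the protocol does not state. No other section of the protocol or visible text of the SAP reverses this.

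The size is unknown because no positive-test rate is given. Under the assumptions shown, bias is about 0.1 to 0.2 points toward no effect on a 3-point difference. Power falls to 80.2% at worst, in a scenario that adds 10% to the existing 15% and ignores earlier visits. A reader might infer a serious threat to the primary result, or an effect that favours SAGE-324; neither follows from these figures. The reason to act is that primary data are lost avoidably, possibly in relation to outcome, and the remedy is cheap.

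**What to change.** **Protocol 9.2.3 and Schedule of Assessments.** Leave the IP-stopping clause untouched and delete the ban on efficacy assessments. At any visit with a positive test, including Day 29, collect TETRAS and Kinesia ONE and flag the record. Put the alcohol screen in the visit order so that TETRAS is done before its result is read. For positives before Day 29, collect TETRAS at least at the EOT visit, as for others who stop IP, and on Day 29 for those who remain on study.

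**SAP.** Carry the flag into the analysis data. State whether alcohol-related withdrawals get the worst value or LOCF in 8.3.3.1.3. Add one sensitivity run of the primary MMRM excluding flagged records. Say in the estimand how these withdrawals are handled.

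**For the sponsor to reconcile.** Section 9.2.3 with 8.4.1 and 8.4.2, on whether a participant with a positive test leaves the study and which follow-up applies. No clinical rule is proposed here.

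**Cost.** One protocol paragraph, a line in the visit order and a few SAP sentences. Some participants attend visits already in the schedule. A few alcohol-affected or off-treatment scores enter the Full Analysis Set; the sensitivity run shows how much the flagged ones matter.
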